### 5.2.3 Planned Statistical Methods

Statistical analyses will be conducted according to a Statistical Analysis Plan (SAP) for the efficacy analyses and a Psychometric Analysis Plan (PAP) for the assessment of psychometric properties of the PEBEQ Item 3 (event-specific bother). These analysis plans will be finalized before the database is “locked”. Statistical analysis will be performed using the SAS system or an equivalent validated analysis system.

#### 5.2.3.1 Missing Data

No individual PEBEQ Item 3 (event-specific bother) data will be imputed.

For each subject, the mean of PEBEQ Item 3 (event-specific bother) responses observed during the baseline period will serve as the baseline period score. In order to continue in the study, the subject must have at least three (3) observations of PEBEQ Item 3 (event-specific bother) in the baseline period. Similarly, the mean of PEBEQ Item 3 (event-specific bother) responses observed during the treatment period will serve as the treatment period score. At least one (1) treatment period PEBEQ Item 3 (event-specific bother) response is required. Subjects who do not have a treatment response for PEBEQ Item 3 (event-specific bother) will be dropped from all efficacy analyses and psychometric analyses concerning the responsiveness to change and meaningful change. The treatment period score must be at least 1 unit larger than the baseline period score for that subject to be considered a “success”.

If a missing IELT for an individual encounter occurs due to anteportal ejaculation (ejaculation happening before penetration), the IELT for that encounter will be set to 0 seconds. If a missing IELT for an individual encounter occurs due to the non-ejaculation (penetration achieved but no ejaculation occurring), the IELT for that encounter will be set to the maximum achieved for that subject.

No safety data will be imputed.

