PLETHORA SOLUTIONS LTD
CLINICAL STUDY PROTOCOL

**A PILOT MULTICENTER, RANDOMIZED, DOUBLE-BLIND STUDY
COMPARING THE PROPORTION OF RESPONDERS TO PSD502 AND TO
PLACEBO USING THE PEBEQ™ IN SUBJECTS WITH PREMATURE
EJACULATION**

Protocol Number:	PSD502-PE-008
Version and Date:	Final Version 1: 06 June 2018 Final Version 2: 14 November 2018 Final Version 3: 14 February 2019 (not issued)
Amendment 1	14 November 2018
Amendment 2	14 February 2019 (not issued)
Amendment 3	24 June 2019
IND Number:	73,513
Investigational Product:	PSD502®
Sponsor:	Plethora Solutions Ltd. [name]
[contact]
Medical Monitor:	[name] MBChB, DipPharmMed
[contact]
E-mail:	[contact]

Confidentiality Statement

The information in this document contains trade secrets and commercial information that is the property of, or under the control of Plethora Solutions Ltd. The information contained herein is privileged or confidential and may not be disclosed unless such disclosure is required by applicable laws or regulations. In any event, persons to whom the information is disclosed must be informed that the information is privileged or confidential and may not be further disclosed by them. These restrictions on disclosure will apply equally to all future information supplied to you, which is indicated as privileged or confidential. This confidentiality statement also applies to data generated during the course of the study.

PROTOCOL SYNOPSIS

Title of the Study: A Pilot Multicenter, Randomized, Double-Blind Study Comparing the Proportion of Responders to PSD502 and to Placebo Using the PEBEQ™ in Subjects With Premature Ejaculation

Coordinating Investigator: [name], [name]

Study Center(s): Up to 30 centers in the United States of America will take part.

Study Population: Male subjects with lifelong premature ejaculation (PE) according to the International Society for Sexual Medicine (ISSM) definition, aged 18 and over, who are at least moderately bothered by their PE, as measured by the Premature Ejaculation Bothersome Evaluation Questionnaire (PEBEQ™) Item 3 (event-specific bother).

Planned Date of First Subject Enrolled: Quarter 4, 2018

Planned Date of Last Subject Completed: Quarter 1, 2020

Objectives:**PRIMARY OBJECTIVE**

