Determine if the PSD502 group has a greater proportion of successful subjects on the PEBEQ Item 3 (event-specific bother) than does the placebo group, where success is defined for each subject as having a mean response over the 4-week treatment period at least 1 point better than the subject's mean response over the 4-week baseline period.

SECONDARY OBJECTIVES

Determine the psychometric properties of PEBEQ Item 3 (event-specific bother). In particular, the consistency in scoring of the PEBEQ Item 3 (event-specific bother) with the Patient Global Impression of Severity (PGI-S), Patient Global Impression of Change (PGI-C), Patient Global Impression of Change-Bother (PGI-C-Bother), Independent Ejaculation Quickness Item (IEQI) and Independent Numeric Response Scale (NRS) Bother Item and its responsiveness to change and derivation of meaningful change (anchor-based and other methods) will be evaluated. Other psychometric properties including reliability (test-retest reproducibility) and validity will also be evaluated.

Determine if the PSD502 group has a greater median score in the PGI-C and the PGI-C-Bother than does the placebo group.

Determine if the PSD502 group has a greater mean increase in the intravaginal ejaculatory latency time (IELT), the PGI-S, the Index of Premature Ejaculation® (IPE) Domain Scores, the Independent NRS Bother Item, and the IEQI than does the placebo group over the course of the study.

Evaluate safety and tolerability of PSD502 in subjects with PE and in their sexual partners.

EXPLORATORY OBJECTIVES

Determine if each of the PEBEQ multi-item scores are improved more in the PSD502 group than in the placebo group.

Other analyses suggested by the data.

Methodology:

This is a pilot, multicenter, randomized, double-blind, placebo-controlled clinical trial to evaluate the efficacy of PSD502 applied to the glans penis on bother-related symptoms secondary to PE. Additionally, psychometric evaluation of PEBEQ Item 3 (event-specific bother) will be investigated.

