Upon completion of the baseline period, subjects will return to the clinic for Visit 2. The diary card will be reviewed, and AE and concomitant medication information will be collected. Those subjects who have a baseline IELT of ≤ 1 minute for all sexual encounters, where each encounter is separated by at least 24 hours and who indicate a level of Bother on Item 3 of the PEBEQ of either "moderately", "quite a bit" or "extremely" on all encounters during the baseline period will be eligible to continue in the study and receive study medication for 4 weeks. Subjects will complete a baseline IPE questionnaire and also have their glans penis visually examined.

If the subject is eligible, he will be stratified into one of two groups, according to whether or not he is circumcised. The subject will be randomized within each stratification group to either PSD502 or placebo (1:1) and will be given sufficient study medication to last until the next clinic visit as well as a new diary card. The subject must be willing to use the study spray for all sexual encounters. The subject will be instructed on how to use the spray and instructed to use it in the next 4 weeks, at least once per week and to leave at least 24 hours between each sexual encounter. For each sexual encounter, the subject will time his IELT using a stopwatch. The subject will record the date and time of sexual intercourse, PEBEQ responses, PGI-S, Independent NRS bother item, IEQI, number of sprays used and IELT data in the diary card. The subject will document efficacy and tolerability data in a diary card and will use the date and time stamper to document the time at which they record details for each sexual encounter. The diary must be completed immediately after the encounter if possible or within 12 hours of the encounter.

At Visit 3, Final Evaluation Visit, the diary card, date and time stamper and any previously dispensed medication will be collected, AE and concomitant medication enquiries will be made and the subject will be asked to complete an IPE questionnaire. The subjects will undergo safety evaluations as for the Screening Visit (Visit 1), including examination of the glans penis. At this last visit, subjects will be asked to provide a PGI-C in the quickness of their ejaculation and will be asked to answer “Was this a meaningful or important change for you?” All subjects will also be asked to complete a PGI-C-Bother and will be asked if the change was meaningful or important.

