The placebo spray will be administered in the same manner as the PSD502 spray.

Criteria for Evaluation:

Efficacy:

The primary efficacy variable is the:

- Success on the PEBEQ Item 3 (event-specific bother), where success is defined as having a 1-point or greater improvement between the mean response over the treatment period and the mean response during the baseline period

The secondary efficacy variables are the:

- PGI-C
- PGI-S
- PGI-C-Bother
- IELT
- IEQI
- Change from baseline in the IPE Control, Distress and Satisfaction Domain Scores
- Independent NRS Bother Item

The exploratory efficacy variables are the:

- PEBEQ Multi-Item Event Specific Subscale Total

- PEBEQ Multi-Item General Subscale Total

Psychometric:

- PEBEQ Item 3 (event-specific bother)

Safety:

Safety variables include study drug exposure, the nature, incidence, relationship and severity of AEs and serious AEs (SAEs), incidence of and reasons for withdrawals, laboratory parameters, use of concomitant medications, vital signs, findings on physical examination, 12-lead ECG and visual examination of the penis.

Statistical Methods

Sample Size: In order to assess the proportion of subjects who achieve a 1-point or greater improvement over 4 weeks in the mean PEBEQ Item 3 (event-specific bother), 100 subjects will be randomized into this pilot study, 50 per arm (allowing for a 10% dropout rate). This sample size is sufficient to detect a difference of 30% in success rates when the placebo rate is 20%, with power 80% using a chi square test with a 5% Type I error rate.

In order to assess the psychometric properties of the PEBEQ Item 3 (event-specific bother), the 100 subjects will be used. This sample size is sufficient to provide estimates of meaningful change; in a validation study conducted on 56 males to test the psychometric performance of the full PEBEQ including the General and Event Specific subscales, the standard error associated with correlations of about 0.50 on a number of patient reported outcomes (PROs) was about 0.12. With a sample size of 100, the standard error is expected to decrease to around 0.05 to 0.08.

Randomization:

A randomization schedule assigning subjects to treatment will be defined for each site and stratified by circumcision status. Each schedule will be blocked, independently of the other schedules.

Analysis Populations:

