All randomized subjects who receive at least one dose of a study drug and who have at least three observations of PEBEQ Item 3 (event-specific bother) in the baseline period and at least one in the treatment period will be included in the modified intent-to-treat (MITT) population.

To adequately assess the reliability and validity of the PEBEQ Item 3 (event-specific bother), all eligible subjects entering the baseline period who indicate a 4 or greater on the Screening 11-point NRS Scale to Assess Bother will be included in the analyses (psychometric population). The PEBEQ Item 3 (event-specific bother) analysis set will consist of all subjects with valid sexual event data completed between screening and randomization.

Safety variables will be evaluated on all subjects who are treated (safety population).

Efficacy Analysis:

The primary response variable is success on the PEBEQ Item 3 (event-specific bother), where success is defined *a priori* as having a 1-point or greater improvement between the mean response over the treatment period and the mean response during the baseline period. Success will be modelled using a generalized linear mixed effects model with treatment, circumcision status and baseline mean PEBEQ Item 3 (event-specific bother) score as fixed effects and site as a random effect. The null hypothesis of no treatment effect will be tested after adjustment for these other covariates.

PGI-C and PGI-C-Bother will be evaluated using a non-parametric test adjusted for site and, circumcision status.

A linear mixed effects analysis model will be used to evaluate treatment effect on IELT during the study. The fixed effects are period (baseline or treatment period), treatment, period-by-treatment interaction and circumcision status and the random effects are site and subject within site.

The same analysis will be conducted on PGI-S, Independent NRS bother item, and IEQI.

A linear mixed effects model will be used to evaluate treatment effect on the change from baseline in each of the IPE domains. The fixed effects are treatment, circumcision status and baseline, while site is the random effect.

Treatment effects will also be evaluated for each circumcision status.

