## 5 STATISTICS

### 5.1 DETERMINATION OF SAMPLE SIZE

In the Plethora study, “Development of the Premature Ejaculation Bothersome Evaluation Questionnaire (PEBEQ): Quantitative Research Stage, 10/56 = 18% of subjects had improvements of 1 unit or more on Item 3 (event-specific bother). This data was collected in the development and testing of the PEBEQ itself. No treatments were involved, so this can be considered to be a control success rate. Treatment change in “distress” scores of the IPE measured throughout the Sponsor study PSD502-PE-002, a double-blind placebo study, appear to support the anticipation of a 30% treatment change in the “bother” score of the PEBEQ in the current pilot study. Although there is no established criterion for a clinically meaningful success rate, it is hoped that treatment will result in more than doubling the success rate in the present study.

Randomizing 100 subjects (50 per treatment arm) is feasible for this pilot study in order to assess the proportion of subjects who achieve a 1-point or greater improvement over 4 weeks in the mean PEBEQ Item 3 (event-specific bother). This sample size is sufficient to detect a difference of 30% in success rates when the placebo rate is 20%, with power 80% using a chi square test with a 5% Type I error rate. It allows for a 10 percent dropout rate.

In order to assess the psychometric properties of the PEBEQ Item 3 (event-specific bother), the 100 subjects will be used. This sample size is sufficient to provide estimates of meaningful change; in a validation study conducted on 56 males to test the psychometric performance of the full PEBEQ including the General and Event Specific subscales, the standard error associated with correlations of about 0.50 on a number of PROs was about 0.12. With a sample size of 100, the standard error is expected to decrease to around 0.05 to 0.08.

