#### Primary objective

The primary response variable is success on the PEBEQ Item 3 (event-specific bother), where success is defined *a priori* as having a 1-point or greater improvement between the mean response over the treatment period and the mean response during the baseline period. Success will be modelled using a generalized linear mixed effects model with treatment, circumcision status and baseline mean PEBEQ Item 3 (event-specific bother) score as fixed effects and site as a random effect. The model assumes a binomial family with logit link. The null hypothesis of no treatment effect will be tested after adjustment for these other covariates in the usual manner. From this model, estimated odds ratio of PSD502 to placebo and the corresponding 95% confidence interval will be calculated. The distributional assumptions of the model will be evaluated to ensure a satisfactory fit prior to statistical estimation and testing.

Additionally, the treatment effect for each circumcision status will be evaluated by adding the treatment-by-circumcision status interaction to the above model. From this model, estimated odds ratio of PSD502 to placebo and the corresponding 95% confidence interval for each circumcision status will be calculated.

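### In the text reviewed, the only success rule with an arithmetic sign asks for a larger Item 3 score, while the primary endpoint is defined as improvement; the two conflict if higher codes mean more bother.

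*SAP*

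**What the plan says.** The protocol and SAP state the success criterion for PEBEQ Item 3 in two ways.

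**By clinical direction, without a sign.**
- The protocol's primary objective describes success as "having a mean response over the 4-week treatment period at least 1 point better than" the subject's own baseline mean.
- The protocol synopsis, under Criteria for Evaluation, says that "success is defined as having a 1-point or greater improvement between the mean response over the treatment period" and the baseline mean. Its Efficacy Analysis paragraph repeats this as the a priori definition.
- SAP section 5.2.3.8, Primary objective, gives the same definition: "having a 1-point or greater improvement between the mean response over the treatment period and the mean response during the baseline period".
- SAP section 5.1 supports the control rate with a development study in which "10/56 = 18% of subjects had improvements of 1 unit or more on Item 3 (event-specific bother").

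**By arithmetic direction.** SAP section 5.2.3.1 (Missing Data) says: "The treatment period score must be at least 1 unit larger than the baseline period score for that subject" to count as a success. The Missing Data part of the protocol synopsis has the identical sentence.

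For Item 3, the text reviewed gives response labels but no numeric codes. SAP section 5.2.2 refers to Section 4.1 for the definition of the efficacy variables. That section was not part of the text reviewed, so the codes may well be stated there.

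**The concern.** A reader deriving the binary endpoint from this text finds a sign in only one place, and that sign is an increase. Item 3 measures bother. On a bother scale whose codes rise with bother, an increase of 1 unit is a deterioration, so the sentence would define success as the opposite of what the primary objective and primary analysis intend.

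The derived variable feeds the primary logistic mixed model, its odds ratio and confidence interval, and the same model with the treatment-by-circumcision interaction. A sign error in the derivation would therefore pass into every primary result.

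**Working it through.** **Step 1: the plan's own sample size.** Inputs from SAP section 5.1: 20% versus 50%, chi-square test, 5% Type I error, 80% power, 10% dropout. A two-sided test is assumed here.
- Without continuity correction: n = [1.960 × √(2 × 0.35 × 0.65) + 0.842 × √(0.20 × 0.80 + 0.50 × 0.50)]² / 0.30² = 38.5, so 39 per arm.
- With continuity correction: (38.5 / 4) × [1 + √(1 + 4 / (38.5 × 0.30))]² = 44.9, so 45 per arm.
- With dropout: 45 / 0.90 = 50 per arm, 100 in total.

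The stated figure is reproduced. It rests on improvement rates, so correcting the sentence leaves it unchanged.

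**Step 2: the two rules side by side.** Let B be a subject's baseline mean and T the treatment-period mean.
- Missing Data sentence: T − B ≥ 1.
- Endpoint definition if higher codes mean more bother: B − T ≥ 1.
- Endpoint definition if higher codes mean less bother: T − B ≥ 1.

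In the first coding, adding the two conditions gives 0 ≥ 2, so no subject can satisfy both rules. In the second coding they are the same rule.

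**Step 3: an illustration under assumed codes 0 to 4, higher meaning more bother.** A subject who goes from 4, 4, 4 to 1, 1, 1 has T − B = −3. He has clearly improved, but he fails the Missing Data rule. A subject who goes from 2, 2, 2 to 4, 4, 4 has T − B = +2. He is worse, but he passes it.

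**Step 4: which coding does the text favour?**
- *Higher means more bother.* The protocol's Visit 2 eligibility text admits subjects "who indicate a level of Bother on Item 3 of the PEBEQ of either" moderately, quite a bit or extremely, an ascending set of labels. The Study Population paragraph describes the same men as those "who are at least moderately bothered by their PE, as measured by the Premature Ejaculation Bothersome Evaluation Questionnaire" Item 3. The screening bother NRS, a different item, also runs upward with bother, because a score of 4 or more is required to show that a subject is bothered.
- *Higher means less bother.* The secondary objectives express benefit as an increase on PGI-S, the Independent NRS Bother Item and IEQI, and as a higher median on PGI-C and PGI-C-Bother. A convention of that kind would fit *larger*.
- *Neutral.* The anchor-based analysis (SAP section 5.2.3.9) describes responders by a decrease in severity. That is verbal and fixes no code for Item 3.

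The first reading is the more natural one, but it is not established.

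**Step 5: size, conditional on higher meaning more bother.** At the planning rates, improvers number 0.20 × 50 + 0.50 × 50 = 35 of 100 randomized, or 0.20 × 45 + 0.50 × 45 = 31.5 of 90 after dropout. All of them would be failures under the Missing Data sentence. The documents give no rate of worsening, so the success rates and treatment difference that sentence would produce cannot be calculated.

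**The case against.** The strongest reply is that the point depends on a coding that the text reviewed does not show. Section 4.1 is cited but was not available, and SAP section 5.2.3.8 indicates that an appendix holds the scoring of at least one instrument, the IPE. If Item 3 is reverse-coded, the wording is consistent. The increase wording in the secondary objectives keeps that possibility open, although its list is headed by IELT, for which an increase really is the benefit, so the phrase may simply have been carried over to the other scales.

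The second reply is that the intent is not in doubt. The primary objective, the efficacy criteria, the synopsis analysis paragraph and the SAP's primary analysis all say better or improvement. The outlying sentence closes a paragraph on missing data. SAP section 5.2.3 also provides for separate analysis plans to be finalized before database lock, which is a natural point to settle the derivation.

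Both replies have force. They rule out a stronger reading that a reader might infer, namely that the primary endpoint is inverted and the trial will count worsening as success. The documents do not support that: the coding is not shown, and the statements of intent make a fully inverted analysis unlikely. What stands is that the only signed rule in the text reviewed is, on the more natural coding, the wrong way round. A later plan does not correct the sentence unless someone changes it.

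**Conclusion.** This is a conditional correction to the primary endpoint definition. If higher Item 3 codes mean more bother, the Missing Data sentence contradicts the endpoint for every subject who changes by 1 point or more. On the plan's own rates, 35 of 100 randomized subjects would be improvers counted as failures. If Item 3 is reverse-coded, there is no contradiction and no misclassification, and only the clarity of the wording is at issue.

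Confidence is medium, because the conclusion rests on label order and descriptive wording rather than on a stated code. A reader might also infer a bias of known size or direction in the treatment comparison. Without a rate of worsening, the documents support neither. Nor is it alleged that the plan omits the Item 3 coding. The sample size of 100 stands under either coding.

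**What to change.** Before database lock, check the Item 3 codes against the questionnaire scoring and make these changes:

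1. In the Missing Data paragraph of the protocol synopsis and in SAP section 5.2.3.1, replace *at least 1 unit larger than* with *at least 1 unit better (less bother) than*.
2. In both places, and in the Primary objective part of SAP section 5.2.3.8, add the one signed formula that matches the coding: baseline mean minus treatment mean ≥ 1 if higher means more bother, or treatment mean minus baseline mean ≥ 1 if reverse-coded.
3. Carry the same formula into the separate SAP.

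The cost is one sentence in each document and a matching line in the primary analysis section. No new data are needed and the sample size does not change. Under SAP section 5.2.3.12, a change after lock would have to be reported with its rationale and a discussion of potential bias; correcting the sentence before lock avoids having to add that bias discussion for the primary endpoint.
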